3.4.8 A randomized, double-blind, placebo-controlled study of RAD001 in the treatment of patients with subependymal giant cell astrocytes (SEGA) associated with Tuberous Sclerosis Complex (TSC)

In the phase I Study CRAD001C2413, (IND #70,714) everolimus was administered orally at a daily dose of 2.1, 3, 5 and 6.5 mg/m² in cohorts of three to six patients per dosage level (Fouladi et al., 2007). The MTD for this population was 5 mg/m². At the starting dose of 3 mg/m² readily reversible grade 3 and 4 dose-limiting toxicities (DLTs) at 3 mg/m² included reversible hypokalemia (n = 1, grade 4) and hypophosphatemia (n = 2, grade 3) were observed in platinum pretreated patients, resulting in dose de-escalation to 2.1 mg/m². The definition of DLT was amended to exclude grade 3 or 4 electrolyte abnormalities that resolved to grade 2 or below within 7

days of interrupting treatment, allowing further dosage escalation. Dose de-escalation to 2.1 mg/m 2 led to no further DLTs in three assessable patients. Three more assessable patients were then enrolled at 3 mg/m 2 and 5 mg/m 2 , each with no DLTs. At 6.5 mg/m 2 , the DLTs included grade 3 events of elevation of ALT (n = 1), mucositis (n = 1), and diarrhea (n = 1). Thus, three more patients were enrolled at 5 mg/m 2 , with no observed DLTs, establishing 5 mg/m 2 as the recommended MTD. No additional grade 4 side effects were reported. Additional grade 3 effects at any time during trial therapy were ALT elevation (1 patient, 5mg/m 2), reduced hemoglobin (2 patients at 3 mg/m 2), infection (3 patients at 3 mg/m 2), leucopenia (2 patients at 3mg/m 2), mucositis (one patient), hypokalemia (1 patient at 3mg/m 2), 1 patient at 5mg/m 2), hyponatremia (1 patient at 3mg/m 2), anorexia (1 patient at 3 mg/m 2), dizziness (1 patient at 3mg/m 2), hyperglycemia (1 patient at 5 mg/m 2). The adverse events seen were consistent with the known safety profile of everolimus in adults.

Everolimus pharmacokinetics in children were also found to be comparable to adults. Everolimus was absorbed rapidly, with maximum concentrations achieved as early as 30 minutes after administration. The maximum everolimus whole-blood concentrations and AUC at each dose level were variable, but increased with dose.

3.4.9 Phase I Study of Everolimus in Pediatric Patients with Refractory Solid Tumors

Everolimus has been investigated in one phase I/II study (28 patients) in patients with TSC who have subependymal giant cell astrocytoma (SEGA) [CRAD001C2485]. Additionally, two phase III studies have been conducted in patients with TSC: study CRAD001M2301 in patients with TSC who have SEGA (117 patients) and study CRAD001M2302 in patients with renal angiomyolipoma (118 patients). CRAD001MIC02 is an ongoing, expanded access phase IIIb study for patients with TSC associated SEGA. Currently, there is a fourth phase III study CRAD001M2304 ongoing in which everolimus will be tested to evaluate whether its use as adjunctive treatment results in reducing seizure frequency in patients with TSC who have refractory seizures.

Data on a small series of TSC patients who had systematic SEGAs which were treated with daily rapamycin therapy showed tumor size reduction by 46-63% within 2.5 to 5 months (Franz et al. 2006). All lesions exhibited regression and, in one case, necrosis. Interruption of therapy for one patient resulted in regrowth of the SEGA, but further regression of another 62-75% was seen upon the resumption of therapy. These results represented a new therapeutic paradigm for the treatment of SEGAs in the TSC patients with rapamycin and related agents.

Therefore, in 2007, everolimus entered clinical development for TSC. Study C2485, conducted by Cincinnati Children's Hospital Medical Center (CCHMC), is a prospective, non-randomized, open-label, investigator-initiated, single-center 28-patient trial designed to evaluate the safety and efficacy of everolimus in patients \geq 3 years of age with SEGA associated with TSC. The primary efficacy endpoint was the change from baseline in volume of primary SEGA lesion at 6 months, as determined by central radiology review. At 6 months, 9 out of 28 patients (32%, 95% CI: 16% to 52%) had a \geq 50% reduction in the tumor volume of their largest SEGA lesion. The median duration of response for these 9 patients was 11.8 months (range 3.2 to 39.1 months). Response rate continues to improve as 58.3% of patients (14 of 23) who took everolimus for at least four years have experienced a reduction of \geq 50% in the size of their largest SEGA relative to baseline. One patient has experienced a SEGA progression (defined as an increase of at least 25% to a value greater than baseline). The median time from first response to progression/censoring was 37 months (range: 6-63 months). No patient developed a new lesion and none required surgical resection or other therapy for SEGA.

The safety and efficacy of everolimus in patients with TSC who have SEGA was studied further in [CRAD001M2301], a randomized (2:1), double-blind, placebo-controlled trial of everolimus conducted in 117 pediatric and adult patients with SEGA and TSC. The main efficacy outcome measure was SEGA response rate based on independent central radiology review. After 6-months of study treatment, 35% of the patients treated with everolimus had at least a 50% reduction in SEGA volume compared to none in the placebo group (Franz et al 2013). Based on recent data, the response rate after at least 12-months of everolimus treatment has increased to 48%. SEGA progression was seen in nine of the all patients treated with everolimus (8.1%). In five patients, progression occurred after cessation of treatment or was associated with C_{min} values which were markedly reduced or at zero. In one case of progression, the patient developed hydrocephalus that was successfully treated, in the absence of SEGA growth. In one case, progression reversed with further treatment.

3.5 Study Rationale

Currently, no effective therapies for individuals with germline PTEN mutations exist to target neurocognitive and behavioral deficits, and effective interventions that target the core biologic alterations are crucial to optimize the short and long-term outcome of individuals affected with mutations in this gene.

Like TSC, PTEN deficiency is an attractive target for treatment with mTOR inhibitors due the PTEN's role through AKT to regulate specifically mTORC1, which is sensitive to rapamycin and analogs such as everolimus.

Use of a neurocognitive composite score to determine efficacy has several advantages. Assuming that everolimus treatment does not impair some functions while improving others, a composite score is likely to be sensitive, highly reliable, can be computed in all patients even if 1 or 2 measurements are missing or could not be completed, and has good domain coverage to capture possible variability across patients in the specific neurocognitive domains showing improvement. An example of the latter advantage, is if some individuals show improvements in processing speed while others show improvements in working memory. The neurocognitive composite would identify improvements in both of these sets of patients. As such, the neurocognitive composite may be more sensitive to change than any individual measure. Furthermore, a composite primary efficacy outcome will not require additional multiple comparison correction.

Exploratory measures were chosen based on their potential to serve as objective outcome measures in future trials. While none of these measures have specific evidence with PTEN mutation cases, they have some data regarding abnormalities within autism or developmental disability populations. In the cases of remote eye gaze tracking, resting EEG, and auditory evoked potentials, these measures are also reasonably inexpensive, can be acquired rapidly, and can be acquired in the majority of PTEN patients.

4 Design and Methods

4.1 Study Rationale

This is a phase II, double-blind, randomized, parallel group, placebo-controlled, three center study evaluating treatment with everolimus versus placebo in 40 patients with PTEN gene mutations, ages 5-45 years (inclusive). It is expected that 60 patients will need to be screened to have 40 who will meet inclusion and exclusion criteria.

There are four different phases in this study: pre-treatment (screening), a 6-month blinded treatment phase, a 6-month open label phase for patients initially randomized to placebo, and a follow-up phase. Each of these phases is described in detail below.

4.2 Pre-Treatment Phase (Screening)

At screening, the investigator or his/her designee will assign a unique number to patients being considered for the study, as outlined in the 7904 Manual of Procedures. The patient/parent must provide a signed Informed Consent Form prior to any study screening evaluations being performed. Once the patient/parent provides a **signed informed consent form** and **eligibility is confirmed (all inclusion/exclusion criteria have been verified)**, the investigator or his/her designee will register the patient for randomization.

Screening evaluations will include demography, relevant medical history/current medical conditions, a physical examination (including a neurological examination), suicidal ideation/behavior assessment, vital signs, laboratory assessments, and other additional study entry evaluations. Primary endpoint neurocognitive data will be collected for screening purposes (SB-5, CPT-3, and Purdue Pegboard Test). Once the patient is confirmed as being eligible to be randomized, the baseline visit will be scheduled to occur within 6 weeks of the screening visit.

Participants will be screened for signs and/or symptoms of cancer. If a patient presents at the screening visit with a mass that may be malignant or benign, the study physician will refer them to the appropriate health care providers. If the mass is benign, and the patient meets all other inclusion/exclusion criteria, the patient may be enrolled in the study. Additional information about cancer screening can be found in the Manual of Procedures.

Participants will be screened for suicidal ideation and/or behaviors using the Columbia Suicide Severity Rating Scale (C-SSRS). Participants that are determined to have significant suicidal ideation and/or behaviors, as

defined in Section 4.6.5, will be ineligible to participate in the trial, and will be referred to the appropriate healthcare provider per the principal investigators discretion.

A complete list of screening evaluations is provided in the schedule of evaluations. All of the above assessments/procedures must be conducted and evaluated prior to randomization.

4.3 Blinded Treatment Phase

All baseline procedures and evaluations should be completed within 6 weeks of the screening visit. If a patient's safety lab results are out of range, and the investigator has reason to believe there were situational factors affecting the values, the screening labs may be repeated. The safety evaluations may be completed at a lab that is geographically close to the participant and either provide the results of that analysis directly to the study team, or a sign a release so the study team can obtain the results from the lab. If a patient's baseline visit is more than 6 weeks after the screening visit the participant must have the safety labs re-drawn and processed, have the physical and neurological exam re-done, and the study team will confirm that there are no changes in the medical history or changes to the patient's current medications. If the screening safety evaluation and/or lab results are out-of-range, the participant will not be eligible to participate in the study. Patients who meet the study eligibility criteria following screening will be randomized to receive everolimus or placebo. The randomization ratio is 1:1, with one patient being randomly assigned to everolimus for every one patient randomly assigned to placebo. Treatment assignment via the RDCRN Members' Website should occur prior to the Baseline visit to allow adequate time for pharmacy preparation. Patients must start treatment within 7 days of the baseline visit, given that the participant still meets all inclusionary criteria and has not developed any exclusionary criteria. The medication should be taken at the same each day with a light, low-fat breakfast (i.e. 8:00 am with light breakfast).

The duration of blinded phase this study is 6 months. Patients will have their first daily dose of everolimus or placebo within 7 days of Visit 2 (baseline) and will continue on treatment for 6 months unless an intolerable toxicity occurs, withdrawal of consent, or investigator decision to discontinue the patient from study treatment.

Starting dose and adjustments are defined in Section. 6.2.

Safety evaluations are routinely performed (visit 3/month 1, visit 5/month 3, and visit 8/month 6). Patients must be in a fasting state at the time of blood sampling for all laboratory evaluations including the lipid profile. Hematology and biochemistry assessments are required at the screening visit, the Month 1 visit, the Month 3 visit, and the Month 6 visit. All blood samples obtained at each visit will be sent to LabConnect, LLC and associated testing facilities for analysis. If safety labs are out of range while the participant is randomized, a clinical assessment by the physician will take place that might include a repeat of blood work. Withdrawal from the study will be considered by the principal investigator if clinically indicated and after discussion with the study team. Complete details regarding all study required safety assessments are provided in Section 7.15.

A PK sample will be collected at the Month 1 visit (one month \pm 14 days from the baseline visit), when possible at steady-state, prior to dose administration during this visit, within 24 \pm 4 hours after the last dose. Participants who receive a dose adjustment after this visit will work with study staff to get another PK sample taken at the study site or locally, by a designated and trained remote health care provider, 2 weeks (\pm 1 week) after the new dose has been taken. A PK sample may also be collected from a patient experiencing an adverse event or side effect. The decision to obtain this sample will be made by the site physician.

Visits 4, 6, and 7 (months 2, 4, and 5) can be in-person, or by phone if that is preferred by the family. If performed by phone, a phone interview will be performed to collect safety and other data, review AEs, and assess changes in mood or behavior. All applicable CRFs will be completed. Modified visits 3, 5, 8 (months 1, 3, and 6) can also be conducted by phone/video conference if the family cannot make it to the study site within the designated window due to extenuating unforeseen circumstances.

Tests that will be conducted during the blinded treatment phase include laboratory tests for safety, physical exams (including a neurological assessment), vital signs, and neuropsychological assessments. If unforeseen circumstances (i.e., unexpected personal reasons) prevent the patient from complying with the established visit schedule, the site can re-schedule the visit (within \pm 14 days of the expected visit date). The reason(s) for any visit or treatment delays will be documented in the CRF for the appropriate visit. All on-site visits (screening,

baseline, month 1, month 3, and month 6) must be completed by the participant, and any missed visits would warrant termination from the study. A summary of the neuropsychological results may be made available at study completion.

At the end of the double-blind phase (or early termination), the treatment code will be broken and the participant will be informed of their assigned treatment arm, using the process outlined in the 7904 Manual of Procedures. Participants who received the active compound will enter the follow-up phase of the study (section 4.5) and will be referred back to their treating physicians. Individuals who were in the placebo group will be invited to enter Phase B, a 6-month open-label extension trial (section 4.4). The inclusion of the open-label phase may increase the acceptability of the project by families and increase their participation in the primary, controlled trial. All participants that received everolimus during the blinded treatment phase will enter the follow-up phase of the trial and will be referred back to their treating physicians. A summary of patient's participation in the study will be provided, if needed.

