If unforeseen circumstances (i.e., unexpected personal reasons) prevent the patient from complying with the established visit schedule, the site can re-schedule the visit (within ± 14 days of the expected visit date). The reason(s) for any visit or treatment delays will be documented in the CRF for the appropriate visit. All on-site visits (month 1, month 3, and month 6) must be completed by the participant, and any missed visits would warrant termination from the study. Under extenuating unforeseen circumstances, visits 3, 5, 8 (months 1, 3, and 6) can be conducted by phone/video conference as a modified visit as to still capture obtainable data and maintain patient safety. A summary of the neuropsychological results may be made available at study completion.

At the final visit of the open label phase, or the 6 month visit, participants will exit the trial. As done in the blinded treatment phase, they will receive a letter

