7.7.6 Study Drug Interruption or Discontinuation

An intent to treat approach will be used. All data acquired prior to termination for the reasons outlined below will be included in the primary analysis unless patient withdraws consent. Every effort will be made to conduct a final study visit with the participant and participants will be followed clinically until, if applicable, all adverse events resolve.

The term "interruption" refers to a patient stopping the study medication during the course of the study, but then re-starting it at a later time in the study (as determined by their study doctor).

The term "discontinuation" refers to a patient's premature and permanent withdrawal from the study treatment. The reason for discontinuation from treatment will be recorded. The patient may discontinue participation in the study for any of the following reasons:

- 1. adverse event(s)
- 2. abnormal laboratory value(s)
- 3. abnormal test procedure result(s)
- 4. protocol deviation
- 5. subject withdrew consent
- 6. Withdrawal by the investigator
- 7. lost to follow-up
- 8. administrative problems
- 9. intercurrent illness or event that precludes further visits to the study site or ability to evaluate disease (e.g.-mental status change, large pleural effusion).
- 10. death

If a patient has discontinued the study drug due to an unacceptable adverse event or an abnormal laboratory value, he/she should not have withdrawal of consent recorded as the reason for discontinuation. Instead, the reason for discontinuation must be recorded as due to adverse event or abnormal laboratory value.

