In objective 2, we will examine whether the everolimus group will show more improvement, compared to the placebo group, on the main neurocognitive efficacy composite outcome. Randomization Group (everolimus versus placebo) differences on the neurocognitive composite will be analyzed using mixed effects (growth curve) modeling, fully utilizing repeated measurements collected at three points (Time: baseline, 3-month follow-up, and 6-month follow-up). A significant interaction between Time and Randomization Group, with the everolimus group showing a more favorable outcome trajectory, will support the primary efficacy hypothesis. Maximum likelihood estimation will be implemented in the Mplus program version 7.2 or above.

Mixed effects (growth curve) model analyses will be conducted following the intention-to-treat principle. Data points that are missing due to subject attrition will be handled assuming that data are missing at random (MAR) conditional on observed information, which is less restrictive than missing completely at random (MCAR) assumed in fixed effects analyses such as ANCOVA and regression analysis. In this procedure, all available cases including the ones with missing information will be included in the analyses. By including every subject who completed at least one assessment, we are not only more likely to conserve power, but also less likely to produce biased effect estimates. In mixed effects analyses, the slope of the outcome will be modeled as the key

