17.1 Power Estimation

This is the first study to evaluate the efficacy of everolimus in patients with a PTEN mutation and ASD/DD. As such, analyses will be predominantly descriptive with the intent of generating plausible hypotheses to be tested in a Phase III confirmatory trial. The planned recruitment sample size of 40 was based on three considerations: 1) the expected recruitment potential of the three sites, 2) a desire to ensure sensitivity to any enrichment in side effects or problems with tolerability in everolimus treated patients, and 3) the need for adequate statistical power in examining primary and secondary efficacy outcomes. Assuming an overall dropout rate of approximately 10%, 44 patients will need to be enrolled to get 40 patients with complete trial data. However, following intent to treat procedures, all patients who are randomized, dosed, and for whom baseline data is collected will be included in statistical analyses. Statistical power considerations for each aim/hypothesis are described below. Except for safety analyses, where only everolimus-treated patients would be expected to show enrichment of dropout or side effects, statistical power estimates are based on one-tailed significance tests with Type 1 error rate of α =.05.

Primary Objective- Safety. The planned sample size of 40 is underpowered to detect small differences in dropout rates or side effects between everolimus versus placebo-treated groups. Statistical power will only be adequate if at least a 35% difference in the proportion of dropout/side effects is observed (1- β ≥.81), assuming a one-tailed Type 1 error rate of α =.05. This is equivalent to 1/20 patients experiencing an adverse event/side effect in the placebo arm and 8/20 in the treated arm. Similarly, statistical power of survival analyses will only be fair (1- β ≥.57) if a hazard ratio of 7.5 is observed, equivalent to a 5% dropout rate in the placebo group versus a 30% dropout rate in the everolimus group. However, because the goal is to maintain sensitivity to any potential enrichment in dropout or side effects, any indicator showing a difference of 10% or greater will be considered a meaningful difference and will be reported.

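### Section 4.3 makes a missed on-site visit grounds for study termination, which cuts off follow-up before Month 6 and adds administrative events to any-reason drop-out

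*Combined protocol and SAP*

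**What the plan says.** **The rule.** Section 4.3 (Blinded Treatment Phase) lists screening, baseline and Months 1, 3 and 6 as on-site visits that must be completed, and adds that "any missed visits would warrant termination from the study". Section 4.4 repeats the clause for the open-label phase.

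**The flexibility.** Section 4.3 lets a visit be rescheduled within 14 days of its due date. It also says: "Modified visits 3, 5, 8 (months 1, 3, and 6) can also be conducted by phone/video conference if the family cannot make it" in the window because of extenuating unforeseen circumstances. In 4.4 the equivalent sentence comes directly after the termination clause: "Under extenuating unforeseen circumstances, visits 3, 5, 8 (months 1, 3, and 6) can be conducted by phone/video conference as a modified visit".

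**Analysis.** Section 7.7.6 states: "An intent to treat approach will be used". It continues: "All data acquired prior to termination for the reasons outlined below will be included in the primary analysis unless patient withdraws consent". Section 17 says: "Mixed effects (growth curve) model analyses will be conducted following the intention-to-treat principle", with gaps from attrition assumed missing at random. Section 17.1 adds that "all patients who are randomized, dosed, and for whom baseline data is collected will be included in statistical analyses". Section 17 singles out the 6-month group difference as of particular interest, and compares drop-out due to side effects and drop-out for any reason.

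**After an early exit.** Sections 4.3 and 7.6 break the treatment code at early termination. Section 4.7 allows unblinding on completion of a follow-up visit 28 days after exit, and lists only medical history, concomitant medications and the DOTES for that visit. Section 7.7.6 asks for the full End of Treatment assessments as soon as possible after study drug is stopped early.

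**The concern.** The clause ends study participation, not just treatment, for a reason that is neither withdrawal of consent nor a safety decision. A single absence at Month 1 or Month 3 can therefore become loss of the end-of-treatment outcome. Visits may be missed because of illness or side effects, so the gap may be related to treatment, and the mixed model has to cover it by assuming missing at random.

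The rule also manufactures events for one of the planned safety comparisons. A participant terminated for non-attendance counts as a drop-out for any reason even if willing to continue. In a 20-patient arm each such event is 1/20 = 5 percentage points, and section 17.1 treats a 10-point difference as meaningful and reportable.

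Finally, the wording leaves room for three sites to act differently. One may accept a video visit as completing Month 3; another may treat it as a missed on-site visit.

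**Working it through.** **1. The plan's own figure.** Section 17.1 gives 80% power for a 0.80 SD Month 6 difference with 20 per arm and one-sided alpha 0.05. For a two-sample t-test the noncentrality is 0.80 × √(20/2) = 2.53 on 38 degrees of freedom, which gives power 0.799. At 0.65 SD the result is 0.646 against a stated 0.65. Both reproduce, and both assume that all 20 per arm have a Month 6 score.

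**2. Power by number scored.** At 0.80 SD, with 19, 18, 17, 15 or 14 per arm, power is 0.781, 0.760, 0.738, 0.689 or 0.661.

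**3. Scores lost to the rule.** Assumptions, none of them from the documents: each of Months 1, 3 and 6 is missed with probability p, independently, and is not rescued by rescheduling or a remote visit. The base is 40 randomized, the maximum in section 1.

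- With the rule, a Month 6 score needs all three visits: 40 × (1 − p)³.
- With continued follow-up it needs only Month 6: 40 × (1 − p).
- The cost of the rule is the difference. A missed Month 6 visit loses its score either way and is not charged to the rule.

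| p per visit | Terminated, 1 − (1 − p)³ | Scores with rule | Scores without | Cost of rule | Power with | Power without |
|---|---|---|---|---|---|---|
| 2% | 5.9% (2.4 of 40) | 37.6 | 39.2 | 1.6 | 0.78 | 0.79 |
| 5% | 14.3% (5.7 of 40) | 34.3 | 38.0 | 3.7 | 0.74 | 0.78 |
| 10% | 27.1% (10.8 of 40) | 29.2 | 36.0 | 6.8 | 0.68 | 0.76 |

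Power is interpolated at half the total per arm. For example, 34.3/2 = 17.15 gives 0.738 + 0.15 × (0.760 − 0.738) = 0.741.

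**4. Any-reason drop-out.** Section 17.1's safety scenario is 1/20 against 8/20 (5% v 40%), with stated power of at least 0.81. The exact one-sided Fisher test gives 0.808. Suppose a background termination rate b applies equally to both arms, so each rate becomes p + b(1 − p). With b = 10% (an assumption):

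- placebo 0.05 + 0.10 × 0.95 = 14.5%
- everolimus 0.40 + 0.10 × 0.60 = 46%

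The difference falls from 35 to 31.5 points and exact power falls to 0.61. Administrative events that are balanced between arms still dilute the comparison.

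**5. Whether a remote visit rescues the score.** In Table 13A the CPT-3, SB-5 and Purdue Pegboard carry no mark allowing remote administration at Month 3 or Month 6. The WRAML-2, PPVT-4 and EVT-2 do. A modified visit keeps a participant in the study but does not supply the three core measures of the composite.

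**The case against.** **The remote-visit sentence may be an exception.** In 4.4 it follows the termination clause and reads that way, and rescheduling within 14 days comes first. On that reading termination arises only when both options fail, and would warrant is softer than must. This stands: a reader might infer a flat contradiction, but the text supports only an unreconciled overlap. What remains open is whether a modified visit counts as completed.

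**Intention-to-treat is kept.** A reader might infer that terminated participants leave the analysis. They do not: 7.7.6 and 17.1 keep their data and the analysis set. The damage is to follow-up and to the missing-at-random assumption.

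**Late outcomes are not all lost.** The End of Treatment battery in 7.7.6 may capture cognition at exit. That is fair, but it is not a Month 6 score, and section 4.7 lists no cognitive testing at its early-termination visit.

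**The primary endpoint is not directly touched.** A reader might infer that missed-visit terminations inflate it. They do not, because it counts drop-out due to side effects, and 7.7.6 says that stopping drug for an adverse event must not be recorded as withdrawn consent. Its reason list has no missed-visit entry, but protocol deviation, administrative problems and an intercurrent event preventing site visits could hold one. Only misattribution, or removal before a side-effect drop-out could occur, reaches the primary endpoint, and neither can be sized.

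**The mixed model uses more than Month 6.** True, and the power figures above are for the cross-sectional test only. However, the composite is measured at baseline, Month 3 and Month 6. A participant terminated for missing Month 1 or Month 3 has neither later scheduled value, so there is no Month 3 score to retain.

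**The open-label clause** in 4.4 cannot affect the randomized comparison. This stands.

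**Conclusion.** The concern holds as a defect in follow-up, moderate in size. Followed as written, section 4.3 ends participation for non-attendance, breaks the code, forgoes the Month 6 score and adds to any-reason drop-out. It does not change who is analysed and does not act directly on the primary endpoint.

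The size depends on a missed-visit rate that the documents do not give. At 2% per visit the effect on power is negligible (about 0.78 v 0.79). At 5% it is noticeable (0.74 v 0.78), and at 10% material (0.68 v 0.76). These figures assume independent misses, no rescue and strict application; rescheduling, or discretion in applying the clause, would reduce them. A 10-point gap in any-reason drop-out needs a net excess of two such terminations in one arm. The direction and size of any bias in the efficacy contrast cannot be derived from the documents.

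**What to change.** - In section 4.3, and in 4.4 for consistency, replace the termination clause: a missed visit is a protocol deviation with missing data, and the participant stays in blinded follow-up.
- State that Month 3 and Month 6 assessments are still attempted after a missed visit: on site for the core composite, remotely only for measures that Table 13A marks as remote-capable.
- State that a modified visit counts as attended.
- Reconcile section 4.7 with 7.7.6 on which assessments are done at early termination.
- In the any-reason drop-out analysis, report non-attendance separately from study withdrawal and from drug discontinuation, with its own reason code.

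Whether study drug continues after a missed safety visit is a separate clinical decision for the sponsor to state.

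The cost is a protocol amendment with the reviews that section 18 requires. The visits and assessments are already in the schedule, so no new procedures are needed.
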